8.3.3. Liver Function Parameters

Subjects with elevated post-baseline ALT, AST or Total Bilirubin that fall into the following categories will be identified. Number and percentage of these subjects will be tabulated for each cohort and in total.

- $\text{AST} \geq 3 \times \text{Upper Limit of Normal range (ULN)}$
- $\text{ALT} \geq 3 \times \text{ULN}$
- $\text{AST} \geq 3 \times \text{ULN}$ or $\text{ALT} \geq 3 \times \text{ULN}$

- $AST \geq 5 \times ULN$
- $ALT \geq 5 \times ULN$
- $AST \geq 5 \times ULN$ or $ALT \geq 5 \times ULN$
- Total Bilirubin $\geq 2 \times ULN$
- $AST \geq 3 \times ULN$ and Total Bilirubin $\geq 2 \times ULN^a$
- $ALT \geq 3 \times ULN$ and Total Bilirubin $\geq 2 \times ULN$
- ($AST \geq 3 \times ULN$ or $ALT \geq 3 \times ULN$) and Total Bilirubin $\geq 2 \times ULN$

Total Bilirubin $\geq 2 \times ULN$ is defined as at least one case of post-dose $\geq 2 \times ULN$ occurred between the first incidence date and 30 days after the last incidence date of $ALT \geq 3 \times ULN$ post treatment. Same rule applies to the last 2 categories.

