## **9.3. Events of Special Interest**

### **9.3.1. Combined Elevations of Aminotransferases and Bilirubin**

Combined elevations of aminotransferases and bilirubin, either serious or non-serious and whether or not causally related, meeting the criteria of a potential Hy's Law case (ALT or AST  $\geq 3 \times$  ULN with simultaneous total bilirubin level  $> 2 \times$  ULN) should always be reported to the Sponsor using a SAVER form with the investigator's assessment of seriousness, causality, and a detailed narrative. In addition, an eCRF for liver toxicity should be completed (See Section 9.5).

If the subject discontinues study drug due to liver enzyme abnormalities, the subject will be followed until the abnormality resolves or is considered stable.

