5.2. Safety Variables

5.2.1. Adverse Events

The following safety variables will be assessed in this study according to the Schedule of Events (Table 3.1.1 and Table 3.1.2) in Section 3.1.

- A Treatment-emergent adverse event (TEAE) is defined as an Adverse Event (AE) that emerges during treatment, having been absent at pretreatment, or reemerges during treatment, having been present at baseline but stopped prior to treatment, or worsens in severity since treatment relative to the pretreatment state, when the AE is continuous. Adverse events will be coded using the Medical Dictionary for Regulatory Activities (MedDRA, Version XX.X), and graded according to the National Cancer Institute (NCI) Common Terminology Criteria for Adverse Events (CTCAE) Version 4.03.
- AEs of Special Interest
 - Interstitial Lung Disease (ILD)
ILD is defined as an acute onset of new or progressive pulmonary symptoms, such as dyspnea, cough or fever.
 - Combined Elevations of Aminotransferases and Bilirubin
Hepatic events, both serious and nonserious, presenting with combined abnormalities meeting criteria for a potential "Hy's law" case [i.e., Alanine

aminotransferase (ALT) or Aspartate aminotransferase (AST) $\geq 3 \times$ ULN, with simultaneous total bilirubin $\geq 2 \times$ ULN].

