For each condition, percentages are based on the number of subjects in the Safety Analysis Set for each cohort with a baseline and at least one post-baseline assessment (that is, n in the first column). Subjects classified as missing have a missing test result.

Source Data: adam.ad b; Listing 16.2.8.1.1

Programming note: do not summarize coagulation parameters.

Programming Note: continue for HRG Low and Overall on the next page

Daiichi Sankyo Pharma Development
Protocol U31278-A-U203

Page x of y

<Run Type> (Data Cut Date: DDMMYY; Data Extraction Date: DDMMYY)

<programe> <run date time>

The following table follows 15.3.4.3:

Table 15.3.4.4: Shift Table of CTCAE Grade in Laboratory Tests - Chemistry
Safety Analysis Set

Source Data: adam.adlb; Listing 16.2.8.1.2

Approved

Daiichi Sankyo Pharma Development
Protocol U31278-A-U203

Page x of y

<programe> <run date time>

<Run Type> (Data Cut Date: DDMMYYYY; Data Extraction Date: DDMMYYYY)

Table 15.3.4.5: Number and Percentage of Subjects with Liver Enzymes (ALT, AST) and Total Bilirubin (TBL) Elevation
Safety Analysis Set

HRG High

Category	Patritumab+ cetuximab + cisplatin or carboplatin (N=xxx)	Placebo + cetuximab + cisplatin or carboplatin (N=xxx)	Total (N=xxx)
Subjects with post-baseline AST			
AST >= 3 x ULN	xx (xx.x)	xx (xx.x)	xx (xx.x)
AST >= 5 x ULN	xx (xx.x)	xx (xx.x)	xx (xx.x)
AST >= 8 x ULN	xx (xx.x)	xx (xx.x)	xx (xx.x)
AST >= 10 x ULN	xx (xx.x)	xx (xx.x)	xx (xx.x)
AST >= 20 x ULN	xx (xx.x)	xx (xx.x)	xx (xx.x)
Subjects with post-baseline ALT			
ALT >= 3 x ULN	xx (xx.x)	xx (xx.x)	xx (xx.x)
ALT >= 5 x ULN	xx (xx.x)	xx (xx.x)	xx (xx.x)
ALT >= 8 x ULN	xx (xx.x)	xx (xx.x)	xx (xx.x)
ALT >= 10 x ULN	x (xx.x)	xx (xx.x)	xx (xx.x)
ALT >= 20 x ULN	xx (xx.x)	xx (xx.x)	xx (xx.x)
Subjects with post-baseline AST or ALT			
AST >= 3 x ULN or ALT >= 3 x ULN	xx (xx.x)	xx (xx.x)	xx (xx.x)
AST >= 5 x ULN or ALT >= 5 x ULN	xx (xx.x)	xx (xx.x)	xx (xx.x)
AST >= 8 x ULN or ALT >= 8 x ULN	xx (xx.x)	xx (xx.x)	xx (xx.x)
AST >= 10 x ULN or ALT >= 10 x ULN	xx (xx.x)	xx (xx.x)	xx (xx.x)
AST >= 20 x ULN or ALT >= 20 x ULN	xx (xx.x)	xx (xx.x)	xx (xx.x)
TBL >= 2 x ULN	xx (xx.x)	xx (xx.x)	xx (xx.x)
Concurrent TBL >= 2 x ULN and AST >= 3 x ULN	xx (xx.x)	xx (xx.x)	xx (xx.x)
Concurrent TBL >= 2 x ULN and ALT >= 3 x ULN	xx (xx.x)	xx (xx.x)	xx (xx.x)
Concurrent TBL >= 2 x ULN and AST or ALT >= 3 x ULN	xx (xx.x)	xx (xx.x)	xx (xx.x)

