Concurrent TBL >= 2 x ULN and AST or ALT >= 3 x ULN and ALP >= 2 x ULN	xx (xx.x)	xx (xx.x)	xx (xx.x)
Concurrent TBL >= 2 x ULN and AST or ALT >= 3 x ULN and ALP <= 2 x ULN	xx (xx.x)	xx (xx.x)	xx (xx.x)

Notes: ULN = Upper limit of normal ranges.

Concurrent is defined as at least one case of post-dose TBL >= 2 x ULN occurred between the first incidence date and 30 days after the last incidence date of the corresponding liver enzyme(s) >= 3 x ULN

Source Data: adam.adlb; Listing 16.2.8.1.1

Programming Note: continue for HRG Low and Overall on the next page

<Run Type> (Data Cut Date: DDMMYYYY; Data Extraction Date: DDMMYYYY)

Table 15.3.5: Summary of Vital Signs and Change from Baseline
 Safety Analysis Set

HRG High						
Vital Sign (units) Visit	Patritumab+ cetuximab + cisplatin or carboplatin (N=xxx)		Placebo + cetuximab + cisplatin or carboplatin (N=xxx)		Total (N=xxx)	
	Result	Change	Result	Change	Result	Change
Systolic Blood Pressure (mmHg)						
Baseline						
n	xx		xx		xx	
Mean	xx.x		xx.x		xx.x	
SD	xx.xx		xx.xx		xx.xx	
Median	xx.x		xx.x		xx.x	
Minimum	xx		xx		xx	
Maximum	xx		xx		xx	
Cycle 1 Day 1						
Pre-infusion						
n	xx		xx		xx	
Mean	xx.x		xx		xx.x	
SD	xx.xx		xx.xx		xx.xx	
Median	xx.x		x x		xx.x	
Minimum	xx		xx		xx	
Maximum	xx		xx		xx	
Post-infusion						
n	xx	xx	xx	xx	xx	xx
...						
Cycle N Day N						
n	xx	xx	xx	xx	xx	xx
Mean	xx.x	xx.x	xx.x	xx.x	xx.x	xx.x
SD	xx.xx	xx.xx	xx.xx	xx.xx	xx.xx	xx.xx
Median	xx.x	xx.x	xx.x	xx.x	xx.x	xx.x
Minimum	xx	xx	xx	xx	xx	xx
Maximum	xx	xx	xx	xx	xx	xx

Notes: The baseline value is defined as the last non-missing value before initial administration of study treatment. Repeated or unscheduled tests are not summarized for each scheduled visit, but are included for summaries of last observation on treatment, maximum and minimum post-baseline values. The End of Treatment value is based on the CRF visit. Last observation on treatment is defined as the last non-missing value on or prior to end of treatment duration + 7.

Source Data: adam.advs; Listing 16.2.8.3.1.

Programming note: continue table for Diastolic Blood Pressure, Pulse Rate, Temperature and Weight

Programming Note: continue for HRG Low and Overall on the next page

<Run Type> (Data Cut Date: DDMMYYYY; Data Extraction Date: DDMMYYYY)

Table 15.3.5: Summary of Vital Signs and Change from Baseline
 Safety Analysis Set

HRG High

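### SAP 8.3.3 sets the bilirubin window of all three combined liver categories by ALT dates alone, so AST-only cases drop out of laboratory counts that the Table 15.3.4.5 footnote would include

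*SAP*

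**What the plan says.** SAP 8.3.3 lists liver abnormalities to be counted from post-baseline laboratory values. The last three are combined categories: AST ≥3 × ULN with total bilirubin ≥2 × ULN, ALT ≥3 × ULN with total bilirubin ≥2 × ULN, and either enzyme ≥3 × ULN with total bilirubin ≥2 × ULN. A note is marked on the first of these, the AST category. Under it, bilirubin qualifies if at least one post-dose value "occurred between the first incidence date and 30 days after the last incidence date of" ALT ≥3 × ULN. The section then adds "Same rule applies to the last 2 categories", which are the ALT and either-enzyme categories. AST dates do not enter the window anywhere in the section.

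The shell for this output, Table 15.3.4.5 in SAP 11.4, has a row "Concurrent TBL >= 2 x ULN and AST >= 3 x ULN". Its footnote closes the window "30 days after the last incidence date of the corresponding liver enzyme(s) >= 3 x ULN".

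The event itself is defined elsewhere by either enzyme. SAP 5.2.1 describes a potential Hy's law case as ALT or AST ≥3 × ULN with simultaneous bilirubin elevation. Protocol 9.3.1 requires "Combined elevations of aminotransferases and bilirubin, either serious or non-serious and whether or not causally related" to be reported to the sponsor when ALT or AST reaches 3 × ULN with raised bilirubin, and Protocol 9.5 repeats the ALT-or-AST criterion.

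**The concern.** The note sits on the AST category but times bilirubin by ALT. If ALT never reaches 3 × ULN there is no first or last date, hence no window, and no bilirubin value can qualify. The subject then drops out of the two combined categories that describe them.

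Combined aminotransferase and bilirubin elevation is one of two adverse events of special interest in SAP 5.2.1, and Table 15.3.4.5 is its laboratory-derived count. SAP 11.2 makes the SAP methods and shells together the framework for outputs to the Data Monitoring Committee, so the conflict could reach ongoing safety review as well as the final report.

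**Working it through.** The plan states no figure to reproduce, so the check applies the two written rules to the same subjects.

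Rule: window = [first date of enzyme ≥3 × ULN, last such date + 30 days]; the category is met if its enzyme criterion is met and any bilirubin ≥2 × ULN falls in the window.

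- SAP 8.3.3 text: the enzyme that sets the window is ALT in all three categories.
- Table 15.3.4.5 footnote: it is AST for the AST row, ALT for the ALT row, and either enzyme for the either-enzyme row.

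The subjects below are hypothetical; values are multiples of ULN. Results are in the order AST / ALT / either-enzyme category.

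| Subject | SAP 8.3.3 text | Table 15.3.4.5 footnote |
|---|---|---|
| A: day 21 AST 4, ALT 2; day 31 bilirubin 2.5 | no / no / no | yes / no / yes |
| B: day 21 ALT 4, AST 2; day 31 bilirubin 2.5 | no / yes / yes | no / yes / yes |
| C: day 21 AST 4, ALT 4, bilirubin 2.5 | yes / yes / yes | yes / yes / yes |
| D: day 21 ALT 4; day 80 AST 4; day 85 bilirubin 2.5 | no / no / no | yes / no / yes |

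**Subject A.** Under the text there is no ALT date, so no window. Under the footnote the AST window is day 21 to 21 + 30 = 51, and day 31 lies inside it.

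**Subject D.** Under the text the window is day 21 to 51, and day 85 is outside. Under the footnote the AST window is day 80 to 80 + 30 = 110 and the either-enzyme window is day 21 to 110; day 85 is inside both.

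**Subjects B and C.** The rules agree. The ALT row is identical under both rules throughout.

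The AST row can also move the other way. With AST raised only on day 21, ALT only on day 80 and bilirubin on day 85, the text's window (day 80 to 110) admits the subject to the AST row, while the footnote's (day 21 to 51) does not. The either-enzyme row can only lose subjects under the text, because the ALT window always lies within the either-enzyme window.

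Size of one subject: 105 subjects at the 1:1 ratio in Protocol 11.10 give 105/2 = 52.5, about 52 per arm, and 1/52 = 1.9%. SAP 11.4 also splits tables by HRG stratum; in HRG-high, 70/2 = 35 per arm and 1/35 = 2.9%. These show what one subject weighs. They are not expected rates.

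**The case against.** **The note is a slip, and each category was meant to use its own enzyme.** That is probably the intent, and it would agree with the shell. It does not rescue the text: the category that carries the note is the AST category, and the note names ALT. Extending the rule to the other two categories cannot put AST into it.

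**The shell has the right rule.** This stands in part. A reader might infer that 8.3.3 governs and that an under-count is the planned result. The documents do not support that: the shell is part of the same SAP, and nothing ranks body text above shells. What is established is a conflict that can change the count.

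**Other outputs would show the case.** A reader might infer that an AST-only subject is never recognised as a potential Hy's law case. The documents do not support that either. SAP 5.2.1 accepts AST alone; Table 15.3.1.10 and Listing 16.2.7.5 take adverse events without citing the 8.3.3 window; Protocol 9.3.1 and 9.5 require a SAVER form, and 9.3.1 a liver-toxicity eCRF. Listing 16.2.8.2.3 shows AST, ALT, bilirubin and ALP by date. The subject also remains in the single-parameter rows of Table 15.3.4.5. These routes are not full substitutes for the combined count. The adverse event tables depend on reporting, and the reporting definition asks for simultaneous bilirubin, whereas the laboratory rule allows 30 days. Subject A, whose bilirubin rises ten days after AST, might not be reported as simultaneous.

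**The consequence is small.** Safety analysis is descriptive under SAP 8.3, no decision rule uses this row, and the discontinuation criteria in Protocol Table 4.1 refer to AST or ALT. All of that stands and limits the reach of the point.

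**Conclusion.** The window definition in SAP 8.3.3 is wrong as written. Followed literally, it omits from the AST and either-enzyme combined categories any subject with AST ≥3 × ULN, bilirubin ≥2 × ULN and ALT always below 3 × ULN, as well as a subject whose AST and bilirubin rise together after an earlier ALT window has closed. It conflicts with the footnote of the table it feeds and with the ALT-or-AST definition used elsewhere in both documents.

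The effect is confined to the combined rows of one laboratory table. How many subjects would be affected is unknown, because no document gives a rate of combined elevations or of AST-only cases. A reader might infer that one lost case would erase the whole hepatic signal; without a rate, that cannot be said. The conclusion assumes only that 8.3.3 is read literally; the subject values in the check are illustrative.

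**What to change.** In the SAP 8.3.3 note, replace the reference to ALT ≥3 × ULN with the corresponding liver enzyme(s) ≥3 × ULN: AST for the AST category, ALT for the ALT category, either for the either-enzyme category. This matches the footnote already in Table 15.3.4.5. It costs one SAP sentence, with no new data and no change to the shell.

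A minor separate point can be settled in the same edit. The bilirubin limit in the event definition is >2 × ULN in Protocol 9.3.1 and 9.5 but ≥2 × ULN in SAP 5.2.1 and 8.3.3. The two differ only for a value of exactly 2 × ULN, but they should be reconciled.

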8.3.4. Vital Signs

Values and change from baseline for vital signs, including systolic blood pressure, diastolic blood pressure, pulse, body temperature, and weight will be summarized by treatment group and scheduled time of evaluation (including end-of-treatment visit), as well as for the maximum and minimum post-treatment values, the values at the end-of-treatment visit, and values for the last observation on treatment for the Safety Analysis Set. Last observation on treatment is defined as the last non-missing value on or prior to end of treatment duration plus 7 days.

Repeated or unscheduled tests will not be summarized for each scheduled visit, but will be included for summaries of maximum and minimum post-treatment values. A comprehensive listing of vital signs will be provided.

8.3.5. ECG

Values and change from baseline for ECG parameters, including heart rate, PR interval, RR interval, QRS duration, QT interval, QTcB ($QT / RR^{**1/2}$), and QTcF ($QT / RR^{**1/3}$), will be summarized for each treatment group and in total at scheduled time of evaluation (including end-of-treatment visit).

In addition, the following notable ECG interval values for each parameter will be evaluated:

QTcB and QTcF:

- New >450 msec
- New >480 msec
- New >500 msec
- Increase from baseline >30 msec
- Increase from baseline >60 msec

Note that “New” implies a newly occurring ECG abnormality. It is defined as an abnormal ECG finding at post-baseline that is not present at baseline, e.g., QTc New > 480 msec implies QTc > 480 msec post-baseline and QTc ≤ 480 msec at baseline.

A subject with multiple occurrences of a newly occurring abnormality is counted only once per abnormality.

The percentage of subjects with newly occurring qualitative ECG abnormalities is based on the total number of subjects who are at risk of developing this abnormality in the category. For each individual abnormal finding, this is defined as the number of subjects with both baseline and post baseline evaluations and a normal value at baseline.

If a QTc record is missing but the records of QT interval and RR are available then QTc should be derived using the formula above. If RR is missing but heart rate (HR) is available, QTc should be derived using the following formulae:

- $QTcF = QT \times (HR/60)^{1/3}$
- $QTcB = QT \times (HR/60)^{1/2}$

Data from ECGs will also be presented in the data listings using the Safety Analysis Set.

8.3.6. Dosing and Extent of Exposure

The number of IV received will be summarized for patritumab, cetuximab, and cisplatin/carboplatin, respectively, for subjects in Safety Analysis Set.

Treatment duration in weeks for patritumab and cisplatin/carboplatin is calculated as (date of the last dose – date of the first dose + 21)/7.

Cycle duration in days is calculated as (date of Day 1 of next cycle – date of Day 1 of present cycle). Cycle duration is not calculated for the last cycle. Average cycle duration will be calculated for each subject.

Treatment duration for cetuximab is calculated as Duration (weeks): (date of the last dose – date of the first dose + 7)/7.

For all study treatment expect carboplatin:

- Total cumulative dose (mg/kg) is defined as the sum of all doses (mg/kg) taken by a subject.
- Total cumulative dose (mg) is calculated as total cumulative dose (mg/kg) x weight (kg).
- Dose intensity (mg/kg/cycle/dose) is calculated as $3 \times (\text{total cumulative dose (mg/kg)} / (\text{Duration (weeks)} \times (\text{number of planned doses/cycle})))$
- Relative dose intensity (%) is calculated as $100 \times (\text{dose intensity} / (\text{planned protocol dose}))$

For carboplatin:

- Total cumulative dose (mg) is defined the sum of all doses (mg) taken by a subject.

- Dose intensity is calculated as $3 \times (\text{total cumulative dose (mg)} / \text{Duration (weeks)})$
- Relative dose intensity (%) is calculated as $100 \times (\text{dose intensity}) / (\text{planned protocol dose (mg)})$ where the planned protocol dose is $5 \times (\text{creatinine clearance} + 25)$ (i.e., target of 5 AUC), and the creatinine clearance is calculated using the modified Cockcroft-Gault equation (Protocol Appendix 17.1).

For the purpose of counting cycle, a subject is considered to be treated in a cycle if they receive the Day 1 dose. Treatment duration (in weeks and cycles), total cumulative dose, dose intensity, relative dose intensity, doses not completed, dose reductions, and number of IV received will be summarized using descriptive statistics, and listed for each subject in the Safety Analysis Set. Average cycle duration and number of cycles delayed, defined as time from last cycle > 21 days,) will be reported for patritumab. Subjects' dose modification will also be listed for patritumab, cetuximab, and cisplatin/carboplatin.

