#### 3.1.2.1. Treatment Administration

[Figure 3.2](#) illustrates the order and timing of the treatments involved.

- Patritumab initial loading dose is 18 mg/kg IV (or placebo) over 60 minutes ( $\pm 10$  minutes) followed in cycle 2 and beyond with a maintenance dose of 9 mg/kg IV over 60 minutes ( $\pm 10$  minutes) every three weeks
  - Infusion time can be extended to a maximum of 120 minutes for subjects unable to tolerate the 60 minute infusion
- Cetuximab initial dose at 400 mg/m^2 IV as a 2-hour infusion followed by 250 mg/m^2 over 60 minutes weekly

One hour after the end of the cetuximab administration (on the weeks when cetuximab and platinum therapy are coadministered) infuse with either:

- Cisplatin at 100 mg/m^2 IV infused over 1 hour, every three weeks up to a maximum of 6 cycles
  - Pretreatment hydration with 2 liters of fluid prior to a cisplatin infusion is recommended and should adhere to institutional standards. Adequate hydration and urinary output must be maintained during the following 24 hours. Other pretreatments such as anti-emetic prophylaxis and post-treatments such as hydration are up to the discretion of the Investigator
  - This can be given in a separate infusion during patritumab and cetuximab infusion

[figure not shown]
OR

- Carboplatin, IV bolus over 30-60 minutes, every 3 weeks for a maximum of 6 cycles. The carboplatin dose will be calculated using the Calvert formula:
  - AUC 5 is the target
  - Carboplatin Dose (mg) = 5 x (glomerular filtration rate [GFR] + 25)
  - Estimated serum creatinine clearance (mL/min) calculated using the modified Cockcroft-Gault equation ([Appendix 17.1](#)) can also be used as an estimate for GFR

- The carboplatin dose is required to be re-calculated for every dosing based on the current GFR (or creatinine clearance as an estimate of GFR as per the protocol).
- Pre- and post-treatments are up to the discretion of the investigator

Note: It is important to use the infusion times given above for cisplatin and carboplatin; however, different infusion durations may be used if local practice dictates otherwise, except during Cycle 1, Day 1 for those subjects participating in the Intense PK sampling.

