**Table 5.2: Dose Delays/Reductions for Toxicities Related to Patritumab**

Grade	Action
1	Continue current dose level
2	Continue current dose level
3	Discontinue patritumab/placebo for up to 3 weeks until the event has recovered to Grade 1 or baseline. a Administer patritumab at a dose that is decreased by one dose level for subsequent cycles. A maximum of 1 dose reduction from the 9 mg/kg IV maintenance dose to 6 mg/kg IV maintenance dose will be permitted. No dose reductions below patritumab 6 mg/kg will be allowed.
4	Discontinue patritumab/placebo for up to 3 weeks until the event recovers to Grade 1 or baseline. a Discuss the event with the sponsor's Medical Monitor or designee before restarting patritumab/placebo. If the investigator and the sponsor's Medical Monitor/designee agree, the weekly maintenance dose will also be decreased from 9 mg/kg IV to 6 mg/kg IV.

a If the subject fails to recover to Grade 1 or baseline and dose must be delayed >3 weeks, the subject will be withdrawn from all study treatment, but should continue to undergo all follow-up evaluations

To receive patritumab, a subject's ANC must be  $\geq 1.5 \times 10^9/L$  ( $\geq 1500/mm^3$ ) and platelet count must be  $\geq 100 \times 10^9/L$  ( $\geq 100,000/mm^3$ ). Patritumab may be withheld for up to 3 weeks to allow cell counts to recover to these values. Dose administration may be delayed no more than 3 weeks to allow for recovery. If the dose is delayed more than 3 weeks, the subject will be withdrawn from study treatment, unless discussed and agreed with the sponsor.

All subjects should be carefully monitored for possible infusion reactions during the administration of patritumab/placebo. If, during infusion, a subject experiences mild to moderate symptoms suggestive of infusion reaction (such as fever and chills, with or without nausea/vomiting, pain, headache, dizziness, dyspnea, hypotension), slow down the infusion up to 120 minutes (see Section 3.1.2.1 for administration of patritumab/placebo). All subsequent infusions should be administered at the same slow rate (up to 120 minutes).

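### SAP 8.3.6 counts the patritumab loading dose but divides by one undefined planned dose, so relative dose intensity is not 100% for full, on-time dosing at every duration; units for cetuximab and cisplatin are also wrong

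*SAP*

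**What the plan says.** Protocol section 3.1.2.1 plans two patritumab doses: "Patritumab initial loading dose is 18 mg/kg IV (or placebo) over 60 minutes", then "followed in cycle 2 and beyond with a maintenance dose of 9 mg/kg IV" every three weeks. Protocol Table 5.2 allows both kinds of departure from that plan: "Discontinue patritumab/placebo for up to 3 weeks until the event has recovered to Grade 1 or baseline" after a Grade 3 event, and "A maximum of 1 dose reduction from the 9 mg/kg IV maintenance dose to 6 mg/kg IV maintenance dose will be permitted".

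SAP section 8.3.6 has a block headed "For all study treatment expect carboplatin" (read: except). In that block:

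- Cumulative dose, in mg/kg, is the sum of every dose taken, so the load counts.
- Dose intensity is 3 × cumulative dose ÷ (weeks × planned doses per cycle).
- "Relative dose intensity (%) is calculated as" 100 × dose intensity ÷ *planned protocol dose*.
- Milligrams are obtained by multiplying the mg/kg total by body weight.

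The divisor is spelled out only for carboplatin ("where the planned protocol dose is" followed by the Calvert expression), as one per-administration dose. The Table 15.1.3 footnote refers back to 8.3.6, so no other definition is available. That table carries mg/kg cumulative-dose and dose-intensity rows across all drug columns. Listings 16.2.5.1.2 and 16.2.5.1.3 show cetuximab and cisplatin in mg/m².

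**The concern.** Relative dose intensity (RDI) should read 100% when the plan is followed and fall below 100% when it is not. Here the numerator reflects a two-level regimen while the divisor is one number. The result therefore depends on how long the subject stayed on treatment, even with perfect dosing, and it depends on which planned dose the programmer chooses.

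Table 15.1.3 reports RDI by arm and supports the secondary safety and tolerability objective. A reader who takes 100% to mean full dosing would be misled under either choice. Cetuximab has the same structure, with 400 mg/m² first and 250 mg/m² weekly after. Separately, a block written in mg/kg does not fit two drugs dosed by body surface area.

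**Working it through.** The SAP states no RDI value, so there is no figure to reproduce. The check applies its formula to defined cases.

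**Inputs.** Patritumab 18 then 9 mg/kg, one dose per 21-day cycle (Protocol 3.1.2.1 and 3.1.5). Duration in weeks = (last dose − first dose + 21)/7 for patritumab and cisplatin, and the same with +7 for cetuximab (SAP 8.3.6). The patritumab divisor is not given, so both planned doses are tried.

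**Full, on-time dosing for n cycles.** Cumulative dose = 18 + 9(n−1) = 9(n+1) mg/kg. Weeks = 3n. Dose intensity = 3 × 9(n+1)/(3n) = 9(n+1)/n. RDI is 100(n+1)/n with divisor 9 and 50(n+1)/n with divisor 18.

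| Cycles | Divisor 9 | Divisor 18 |
|---|---|---|
| 1 | 200% | 100% |
| 2 | 150% | 75% |
| 6 | 117% | 58% |
| 11 | 109% | 55% |

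**Departures from plan, divisor 9.** The planned dose over the elapsed time is 18 + 9(weeks/3 − 1).

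| Case | Given (mg/kg) | Weeks | SAP RDI | Planned in that time (mg/kg) | Given ÷ planned |
|---|---|---|---|---|---|
| Six cycles, one maintenance infusion missed | 54 | 18 | 3×54/18/9 = 100% | 63 | 85.7% |
| Six doses, one 3-week delay | 63 | 21 | 3×63/21/9 = 100% | 72 | 87.5% |
| Six cycles, 6 mg/kg from cycle 3 | 18+9+24 = 51 | 18 | 3×51/18/9 = 94.4% | 63 | 81.0% |

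The first result does not depend on six cycles. One missed maintenance infusion before the last dose leaves 9(n+1) − 9 = 9n mg/kg over 3n weeks, so dose intensity is 9 and RDI is 100% for any n of 3 or more. The extra 9 mg/kg in the load exactly replaces the missed dose.

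**Cetuximab, m weekly doses, three planned per cycle.** Cumulative dose = 400 + 250(m−1) = 250m + 150 mg/m². Dose intensity = 3(250m + 150)/(3m) = 250 + 150/m. With divisor 250, RDI = 100 + 60/m %: 103.3% at 18 doses and 101.8% at 33.

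**Cisplatin, c cycles.** 3 × 100c/(3c) ÷ 100 = 100%. With one planned dose level the SAP formula works.

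**Units.** If the mg/m² values in the listings were put through the mg line, the result would be too large by weight ÷ body surface area. For assumed bodies from 50 kg and 1.5 m² to 90 kg and 2.1 m², that is 33 to 43 times.

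**The case against.** The SAP leaves the divisor open, so this could be called an ambiguity that a competent programmer would resolve. If the mean planned dose over the subject's own cycles were used, full dosing would read 100%. That is true, but the text does not say it, and its only worked definition (carboplatin) is a single per-administration dose. Both planned doses that the protocol names give a wrong figure.

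A reader might infer that dose modifications disappear from the report. The documents do not support this. The masking applies to divisor 9 only; divisor 18 errs the other way and understates full dosing. Table 15.1.3 also has rows for number of infusions, cycle duration, delayed cycles and dose reductions. Table 15.3.1.1 counts adverse events leading to patritumab interruption or reduction, and Listing 16.2.5.1.1 shows each infusion. The reduced-dose case reads 94% against 117% for full dosing, so even RDI shows it in part. In the delay case the subject received all 63 mg/kg of six cycles; the 87.5% is relative to elapsed time.

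A reader might also infer a between-arm artefact: if patritumab prolongs treatment, its arm would read lower at equal dosing. With divisor 9, full dosing and exponential time on treatment at the design medians of 4.2 and 7.5 months, the arm means would be 126.9% (control) and 118.3% (patritumab), about 8.6 points apart. That needs all of those assumptions and a true design effect. On medians (7 and 11 doses) the values are 114.3% and 109.1%, about 5 points apart. Both arms read above 100%, equal PFS removes the gap, and no safety inference is planned. It is not a finding.

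On units, mg/kg × kg does give mg if the data really are in mg/kg, and the listings carry the right unit. The inflated figure arises only if mg/m² data go through that line. The inconsistency between section 8.3.6 and the listings remains.

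**Conclusion.** The point holds as a minor, wrong-as-written definition. For patritumab neither planned dose makes RDI 100% at every duration under perfect dosing: 117% or 58% at six cycles. If 9 mg/kg is used, one missed maintenance infusion or one 3-week delay reads 100%, against 86% and 88% of the dose planned over the elapsed time in the six-cycle and six-dose cases. Cetuximab is affected in the same way but by only a few points beyond the first weeks. Cisplatin RDI is correct. The mg/kg labels and the weight multiplication do not fit cetuximab or cisplatin.

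These figures follow from the SAP formula and the protocol doses. The only open input is the patritumab and cetuximab divisor. The consequence is confined to descriptive exposure rows in Table 15.1.3. No PFS analysis, significance level or sample size depends on them.

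**What to change.** In SAP 8.3.6, define RDI (%) as 100 × cumulative dose given ÷ cumulative dose planned over the elapsed treatment duration, with planned totals:

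- patritumab/placebo: 18 + 9 × (weeks/3 − 1) mg/kg;
- cetuximab: 400 + 250 × (weeks − 1) mg/m²;
- cisplatin: no change to RDI.

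The planned total must run over elapsed weeks, not over doses received; otherwise a missed infusion still reads 100%. Full on-time dosing then gives 100% at every n, and the three patritumab cases give 85.7%, 87.5% and 81.0%. Doses withheld after the last infusion remain uncounted, because duration ends 21 days after the last patritumab dose; a footnote can say so.

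Express cetuximab and cisplatin in mg/m² in 8.3.6 and in the cumulative-dose and dose-intensity rows of Table 15.1.3, and do not obtain their milligrams by multiplying by weight. Dropping the mg row for these two drugs is simplest.

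The cost is a few lines in 8.3.6 and some unit labels in one table shell. The RDI change uses doses and dates the section already requires, so no new data are needed.
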